11.1.2.3 Additional procedures for reporting serious adverse events

If an SAE is reported, UCB must be informed within 24 hours of receipt of this information by the site (see contact information for SAE reporting listed in the SAE Reporting section at the front of the protocol). The Investigator must forward to UCB (or its representative) a duly completed “Investigator SAE Report Form for Development Drug” (SAE report form) provided by UCB, even if the data are incomplete, or if it is obvious that more data will be needed in order to draw any conclusions. Information recorded on this form will be entered into the global safety database.

An Investigator SAE report form will be provided to the Investigator. The Investigator SAE Report form must be completed in English.

It is important for the Investigator, when completing the SAE report form, to include the assessment as to a causal relationship between the SAE and the IMP administration. This insight

from the Investigator is very important for UCB to consider in assessing the safety of the IMP and in determining whether the SAE requires reporting to the regulatory authorities in an expedited manner.

Additional information (eg, autopsy or laboratory reports) received by the Investigator must be provided within 24 hours. All documents in the local language must be accompanied by a translation in English, or the relevant information included in the same document must be summarized in the Investigator SAE report form.

The Investigator is specifically requested to collect and report to UCB (or its representative) any SAEs (even if the Investigator is certain that they are in no way associated with the IMP), up to 6 months from last IMP intake for each subject (ie, until the 6-month follow-up echocardiogram), and to also inform participating subjects of the need to inform the Investigator of any SAE within this period. Serious AEs that the Investigator thinks may be associated with the IMP must be reported to UCB regardless of the time between the event and the end of the study.

Upon receipt of the SAE report form, UCB will perform an assessment of expectedness of the reported SAE. The assessment of the expectedness of the SAE is based on the IB.

11.1.3 Follow up of adverse events

An AE should be followed until it has resolved, has a stable sequelae, the Investigator determines that it is no longer clinically significant, or the subject is lost to follow up.

If an AE is ongoing at the end of the study for a subject, follow up should be provided until resolution/stable level of sequelae is achieved, or until the Investigator no longer deems that it is clinically significant, or until the subject is lost to follow up. If no follow up is provided, the Investigator must provide a justification. The follow up will usually be continued for 30 days after the subject has discontinued his/her IMP.

Information on SAEs obtained after final clinical database lock will be captured through the Patient Safety (PS) database without limitation of time.

11.1.4 Pregnancy

If an Investigator is notified that a subject has become pregnant after the first intake of any IMP, the Investigator must immediately notify UCB's PS department by providing the completed Pregnancy Report and Outcome form (for contact details see SAE reporting information at the beginning of this protocol). The subject should be withdrawn from the study as soon as pregnancy is known (by positive urine pregnancy test), and the following should be completed:

- The subject should return for an EDV.
- The subject should immediately stop the intake of the IMP or be tapered as instructed at the EDV.
- An SFU Visit should be scheduled 1 week after the subject has discontinued her IMP.

The Investigator must inform the subject of information currently known about potential risks and about available treatment alternatives.

The pregnancy will be documented on the Pregnancy Report and Outcome form provided to the Investigator. The progression of the pregnancy and the eventual birth (if applicable) must be followed up using the Pregnancy Report and Outcome form in which the Investigator has to report on the health of the mother and of the child. Every reasonable attempt should be made to follow the health of the child for 30 days after birth for any significant medical issues. In certain circumstances, UCB may request that follow up is continued for a period longer than 30 days. If the subject is lost to follow up and/or refuses to give information, written documentation of attempts to contact the subject needs to be provided by the Investigator and filed at the site. UCB's PS department is the primary contact for any questions related to the data collection for the pregnancy, eventual birth, and follow up.

In cases where the partner of a male subject enrolled in a clinical study becomes pregnant, the Investigator or designee is asked to contact the subject to request consent of the partner via the Partner Pregnancy Consent form that has been approved by the responsible IRB/IEC and should be available in the Investigator site file. In case of questions about the consent process, the Investigator may contact the UCB/contract research organization (CRO) contract monitor for the study. The Investigator will complete the Pregnancy Report and Outcome form and send it to UCB's PS department (for contact details see SAE reporting information at the beginning of this protocol) only after the partner has agreed that additional information can be captured and has provided the signed Partner Pregnancy Consent form. UCB's PS department is also the primary contact for any questions related to the data collection for the partner pregnancy, eventual birth, and follow up.

A pregnancy becomes a SAE in the following circumstances: miscarriage, abortion (elective or spontaneous), unintended pregnancy after hormonal contraceptive failure (if the hormonal contraceptive was correctly used), ectopic pregnancy, fetal demise, or any congenital anomaly/birth defect of the baby. Those SAEs must be additionally reported using the Investigator SAE Report form.

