The study is comprised of the following periods: a 4-week Baseline Period; a 16-week Treatment Period consisting of a 3-week Titration Period followed by a 1-week Stabilization Period and a 12-week Maintenance Period; a 3-week Conversion Period for all subjects who choose to enroll in the open-label extension (OLE) study, EP0093, at the end of the Maintenance Period; or a 4-week Taper Period, in case the subjects discontinue or do not enroll in EP0093. During the Titration Period, the investigational medicinal product (IMP) will be increased approximately every 3 to 7 days depending on the treatment arm. For subjects with tolerability issues at their target dose, 1 fallback option to a predefined lower dose will be allowed during the Stabilization Period. During the entire 12-week Maintenance Period, the dose of IMP and concomitant AEDs must remain stable. Subjects who withdraw from the study or decide not to participate in the OLE study will be progressively tapered off the IMP. Safety follow up for these subjects will consist of 1 Safety Follow-up (SFU) Visit 30 days after the last IMP intake (including an echocardiogram) and a 6-month follow-up echocardiogram, depending on the duration of exposure to IMP.

The assessment of efficacy is based on seizure frequency. For the US Food and Drug Administration (FDA), Pharmaceuticals and Medical Devices Agency (PMDA), and other regulatory authorities not specified in Section 4.1.1.2, the primary efficacy variable is the change from Baseline in log-transformed observable focal-onset seizure frequency (for the purpose of this protocol defined as Types IA1, IB, and IC, according to the International League Against Epilepsy [ILAE] classification [ILAE Classification of Epileptic Seizures, 1981]) over the 12-week Maintenance Period. For the European Medicines Agency (EMA) and regulatory authorities who reference EMA, the primary efficacy variable is the 75% responder rate, where a responder is a subject experiencing a $\geq 75\%$ reduction in observable focal-onset seizure frequency from Baseline, over the 12-week Maintenance Period.

Secondary and other efficacy variables will allow further exploration of the effect of PSL on seizure frequency during the entire Treatment Period, seizure severity, quality of life, Hospital Anxiety and Depression Scale (HADS) score, health-related outcomes, and healthcare resource

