4.2.2 Other safety variables

Other safety variables are as follows:

- Incidence of TEAEs reported by the subject and/or caregiver or observed by the Investigator during the following periods: 16-week Treatment Period, 12-week Maintenance Period, 4-week Titration/Stabilization Period, and 3-week Taper Period
- Number of and reason for subjects requiring premature tapering due to TEAEs
- Number of and reason for subjects requiring a dose reduction during the Stabilization Period due to TEAEs
- Incidence of treatment-emergent SAEs during the following periods: 16-week Treatment Period, 12-week Maintenance Period, 4-week Titration/Stabilization Period
- Changes in clinical laboratory test parameters (including hematology, blood chemistry, and urinalysis)
- Changes in vital sign parameters (including pulse rate, systolic BP, diastolic BP, and respiratory rate)
- Changes in 12-lead ECG parameters
- Physical examination (including body weight) and neurological examination findings
- Changes in Psychiatric and Mental Status
- Occurrence of valvular abnormalities or pericardial effusion changes or other significant abnormalities as identified by 2-dimensional Doppler echocardiogram at each assessment by central reader
- Changes in withdrawal symptoms using Clinical Institute Withdrawal Assessment-Benzodiazepines (CIWA-B) from the End of Treatment Visit (Visit 7) to end of the Taper Period (Visit 8) and end of the SFU Period (Visit 9 [30 days after the last IMP intake]).

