At Visit 4 (at the end of the Stabilization Period), subjects will enter a 12-week Maintenance Period during which they will receive their target dose (or their fallback dose, if applicable). During the entire 12-week Maintenance Period, the dose of IMP (target dose or fallback dose) and concomitant AEDs must remain stable. Subjects must return to the clinic for scheduled visits as outlined in [Table 5-1](#).

Subjects who complete the Maintenance Period will return for an End of Treatment Visit. Subjects who discontinue early from the study will return for an Early Discontinuation Visit (EDV). Subjects completing the Maintenance Period will have the opportunity to enroll into the OLE study, EP0093. They will be converted to the entry dose of the EP0093 study, 400mg/day. Subjects withdrawing from the study or deciding not to participate in the OLE study (EP0093) will be progressively tapered off the IMP.

For subjects discontinuing the study:

Taper Period (4 weeks)

The 4-week Taper Period will be required for subjects who choose not to enroll in the OLE study or who discontinue prior to the end of the Maintenance Period. Subjects participating in the 4-week Taper Period should be gradually tapered off the IMP over a 3-week period (Table 7-3) followed by 1-week drug-free period. A faster or slower taper schedule than the suggested 3 weeks may be implemented, if medically necessary, as per the Investigator's medical judgement. Subjects will start their taper at the EDV/End-of-Treatment (Visit 7) and will return 1 week after last intake of IMP for the End-of-Taper Visit at Visit 8. Changes to concomitant AED(s) are not allowed during the taper of PSL unless they are medically necessary as per the Investigator's medical judgement to treat rebound seizures.

Safety Follow-Up Period

Safety follow up for subjects not entering the OLE will consist of 1 required visit, 30 days after the last IMP intake (Week 23 or sooner in case of early discontinuation) including an echocardiogram. An additional follow-up echocardiogram will be performed at 6 months (± 1 month) after the last IMP intake only for subjects exposed to IMP for more than 3 weeks.

For subjects continuing to the OLE study:

Conversion Period (3 weeks)

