- ^j The echocardiogram will be conducted at Visit 1. Echocardiograms will be repeated at Visit 6 for subjects continuing the OLE study. Subjects discontinuing will have an echocardiogram 30 days after last IMP intake at the SFU Visit (except if performed at Visit 6). A repeat echocardiogram will be performed for subjects with a new finding, Grade 2 (moderate severity), or Grade 3 (severe severity).
- ^k An echocardiogram will also be performed 6 months after last IMP intake for subjects exposed to >3 weeks to IMP and discontinuing the study (but not for subjects with <3 weeks exposure).
- ^l AED samples will ideally be taken immediately prior to dose of concomitant medication on each occasion. If this is not possible, then the sample may be taken at any time after dose and the timing of sample in relation to dose should be kept the same (± 1 hour) on each occasion for each subject. Therefore, the timing of visits for each subject when AED samples are collected should be scheduled approximately at the same time whenever possible. Assay of parent PSL and metabolites may be included in the AED panel of tests at Visits 6 and 7.
- ^m On Visits 6 and 7, unless the concomitant AED sample is within ± 5 minutes of a scheduled MITRA sample for PSL assay, a separate, additional MITRA sample will be taken at same time as the concomitant AED blood sample.
- ⁿ Subjects are requested to provide blood samples for measurement of PSL and metabolites whenever possible. On Visits 3, 5, and 6, site personnel should obtain blood samples for measurement of random PSL levels at any time between IMP intake and record accurately the time of last IMP intake and the time of sample collection. On Visits 4 and 7, blood samples for measurement of sparse PK profiles will be collected as follows: immediately before IMP intake (maximum 15 minutes before intake) and then 3 times after (between 30 minutes and 3 hours after IMP intake), taken at least 30 minutes apart. All samples may be taken either at home or in the site or partly at home and partly at the site.
- ^o For all female subjects, serum pregnancy test at Visits 1 and 7 (in case the subject enters into the OLE study) and where applicable. Urine pregnancy test will be used at other visits for female subjects of childbearing potential.
- ^p Seizure counts are collected on the subject's daily record card on a daily basis.
- ^q At each visit following an IMP dispensation, IMP should be presented to check for compliance.

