6. Subjects having on average ≥ 4 spontaneous and observable focal-onset seizures per 28 days (based on Investigator assessment of subject report) with at least 1 seizure during each 4-week interval of the 8-week retrospective Baseline Period prior to entry. Additionally, subjects must experience ≥ 4 spontaneous and observable focal-onset seizures per 28 days (based on Investigator assessment of subject report) during the 4-week Baseline Period.
7. Subject has failed to achieve seizure control with ≥ 4 tolerated and appropriately chosen prior AEDs, including past and ongoing treatment, that were individually optimized for adequate dose and duration. Prior discontinued AED treatment would need to be assessed by the Investigator considering the patient medical records and patient and/or caregiver interview. "Prior AED" is defined as all past and ongoing AED treatments with a start date before the Screening Visit (Visit 1).

Concomitant epilepsy treatment

8. Subject is currently treated with an individually optimized and stable dose of at least 1 and up to 3 AEDs for the 8 weeks prior to the Screening Visit (Visit 1) with or without additional concurrent vagus nerve stimulation (VNS) or other neurostimulation treatments. The latter will not be counted as AEDs for the purpose of eligibility.

Laboratory parameter

9. Subject has clinical laboratory test results within the reference ranges of the laboratory or isolated test results that are outside the specified ranges and that are deemed as not clinically significant by the Investigator.

Birth control

10. Female subjects of child bearing potential must have a negative serum pregnancy test at the Screening Visit (Visit 1), which is confirmed to be negative by urine testing prior to the first dose of IMP at Day 1 (Visit 2) and prior to further dispensing at each study visit thereafter. Subjects will be withdrawn from the study as soon as pregnancy is known.

Female subjects will use an efficient form of contraception for the duration of the study for a period of 3 months after their last intake of IMP. Hormonal contraception may be susceptible to an interaction with the IMP, which may reduce the efficacy of the contraception method. The potential for reduced efficacy of any hormonal contraception method requires that a barrier method (preferably male condom) also be used.

Birth control methods considered as an efficient form of contraception:

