- Seizure evaluation (count and type) from subject's daily record card
- Record concomitant medication (AEDs and non-AEDs) and procedures
- Record AEs
- Record health-related outcomes and HRU (refer to [Section 9.5](#) for details), with the exception of socio-professional status
- Dispense IMP using IRT
- Check IMP accountability
- Perform exit personal outcomes interview/survey (at Visit 6 or can be done at Visit 7) if the subject/caregiver consented to take part in this activity

8.2.3.3 Visit 7 (Week 16 \pm 1 week for End-of-Treatment or earlier for Early Discontinuation Visit)

The following procedures will be performed:

- Verification of withdrawal criteria
- Obtain C-SSRS data since the last visit
- Obtain HADS data
- Obtain SSG data
- Obtain QOLIE-31-P data
- Obtain CIWA-B data (only for subjects tapering)
- Measure vital signs (pulse rate, systolic BP blood, diastolic BP, and respiratory rate), in supine position after 5 minutes of rest
- Measure body weight
- Perform full physical examination (refer to [Section 11.3.4](#) for details)
- Perform full neurological examination (refer to [Section 11.3.5](#) for details)
- Perform Psychiatric and Mental Status assessment
- Obtain 12-lead ECG
- Collect blood and urine samples for clinical laboratory analyses
- Collect blood sample for concomitant AED assay including an additional MITRA sample if the AED sample is not within ± 5 minutes of 1 of the scheduled PSL PK samples

- Obtain MITRA blood samples immediately before IMP intake (maximum 15 minutes before IMP intake) and then 3 times after (between 30 minutes and 3 hours after IMP intake) taken at least 30 minutes apart.
- Obtain blood samples for RNA, protein, lipids, and metabolites
- Perform urine pregnancy test (for female subjects of childbearing potential discontinuing the study only) and serum pregnancy test (for female subjects continuing in the OLE study)
- Seizure evaluation (count and type) from subject's daily record card
- Record concomitant medication (AEDs and non-AEDs) and procedures
- Record AEs
- Record health-related outcomes and HRU (refer to [Section 9.5](#) for details)
- Dispense IMP using IRT
- Check IMP accountability
- Perform exit personal outcomes interview/survey (if not done at Visit 6) if the subject/caregiver consented to take part in this activity

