8.3.2 Visit 8 (Week 19/20 \pm 1 week, end of Taper/Conversion)

The following procedures will be performed:

- Obtain C-SSRS data since the last visit
- Obtain CIWA-B data only for subjects tapering
- Measure vital signs (pulse rate, systolic BP, diastolic BP, and respiratory rate), in supine position after 5 minutes of rest
- Measure body weight
- Perform full physical examination (refer to [Section 11.3.4](#) for details)
- Perform full neurological examination (refer to [Section 11.3.5](#) for details)
- Perform Psychiatric and Mental Status assessment
- Obtain 12-lead ECG
- Collect blood and urine samples for clinical laboratory analyses
- Perform urine pregnancy test (female subjects of childbearing potential only)
- Seizure evaluation (count and type) from subject's daily record card
- Record concomitant medication (AEDs and non-AEDs) and procedures

- Record AEs
- Record health-related outcomes and HRU (refer to [Section 9.5](#) for details), with the exception of socio-professional status
- Check IMP accountability
- Study termination (only for subjects enrolling in OLE study, EP0093)

8.4 Safety Follow-Up (Visit 9 [Week 23 or earlier for EDV, approximately 30 days after last IMP intake])

The following procedures will be performed:

- Obtain C-SSRS data since the last visit
- Obtain HADS data
- Obtain SSG data
- Obtain QOLIE-31-P data
- Obtain CIWA-B data
- Measure vital signs (pulse rate, systolic BP, diastolic BP, and respiratory rate), in supine position after 5 minutes of rest
- Measure body weight
- Perform brief physical examination (refer to [Section 11.3.4](#) for details)
- Perform brief neurological examination (refer to [Section 11.3.5](#) for details)
- Perform Psychiatric and Mental Status assessment
- Obtain 12-lead ECG
- Obtain echocardiogram for subjects discontinuing the study (except if performed at Visit 6)
- Collect blood and urine samples for clinical laboratory analyses
- Perform urine pregnancy test (female subjects of childbearing potential only)
- Seizure evaluation (count and type) from subject's daily record card
- Record concomitant medication (AEDs and non-AEDs) and procedures
- Record AEs
- Record health-related outcomes and HRU (refer to [Section 9.5](#) for details), with the exception of socio-professional status
- End of diary recording
- Study termination, only for subjects who do not enter EP0093

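### Protocol 11.1.4 sets the Safety Follow-up Visit at 1 week for a subject withdrawn for pregnancy, against the protocol's single follow-up visit at about 30 days

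*Protocol*

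**What the plan says.** Protocol 11.1.4 lists what happens when a subject is withdrawn for pregnancy. She returns for an Early Discontinuation Visit, then either stops IMP at once or tapers, and then: "An SFU Visit should be scheduled 1 week after the subject has discontinued her IMP".

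The general rule appears in several places in the current text:

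- Protocol section 1, for subjects who withdraw or do not enter the extension: "1 Safety Follow-up (SFU) Visit 30 days after the last IMP intake (including an echocardiogram").
- Protocol 4.2.2, which identifies the visit by number: "end of the SFU Period (Visit 9 [30 days after the last IMP intake"]).
- Protocol 5.1, for all subjects not entering the extension: "1 required visit, 30 days after the last IMP intake (Week 23 or sooner in case of early discontinuation").
- Protocol Table 5-1, footnote j: "Subjects discontinuing will have an echocardiogram 30 days after last IMP intake at the SFU Visit (except if performed at Visit 6").
- Protocol 8.4, whose heading gives Visit 9 as roughly 30 days after last intake and covers early discontinuation.
- Protocol 5.1.2, SAP Table 3-1 and SAP 10.2, which use the same 30 days.

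Two provisions make the SFU Visit a closing event. Protocol 8.4 attaches the end of diary recording and study termination to it, and Protocol 11.1.1.1 runs adverse event recording up to it.

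**The concern.** A site handling a pregnancy withdrawal will look to 11.1.4 first. That section names an SFU Visit at 1 week. It does not say that the visit is additional to Visit 9, or that Visit 9 still follows at 30 days. Since the protocol otherwise has only one SFU Visit, a site could reasonably treat the 1-week visit as that visit and close the subject there.

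What could be lost is prospective recording of new non-serious adverse events and of seizures in the weeks after dosing stops. That interval has some clinical interest here. Section 11.1.4 allows an immediate stop, whereas other discontinuing subjects normally taper over 3 weeks. Padsevonil is a partial agonist at benzodiazepine sites (Protocol 2.2), and Protocol 7.2.2 and 11.3.8 ask for monitoring of withdrawal symptoms and seizures during taper.

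**Working it through.** This is a consistency check, so the arithmetic is calendar arithmetic. The inputs are the end of treatment at Week 16 (Table 5-1), a 3-week taper (5.1 and 7.2.2), SFU at 30 days (5.1) and SFU at 1 week (11.1.4). I take the day IMP is discontinued to be the day of last intake.

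1. **Reproduce the plan's own figure.** For a completer who tapers, last intake is at about Week 16 + 3 = Week 19. The SFU Visit then falls at 19 + 30/7 = 23.3, that is Week 23, as stated in 5.1 and 8.4. The 30-day rule is therefore consistent with the visit calendar.

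2. **Apply the 11.1.4 rule to the same calendar.** 19 + 1 = Week 20. This is not a Visit 9 slot. Section 5.1 already places the End-of-Taper Visit, Visit 8, 1 week after last intake, so for a pregnant subject who tapers the 11.1.4 visit coincides with Visit 8.

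3. **Size of the gap.** 30 − 7 = 23 days (days 8 to 30 after last intake) if the site closes the subject at the 1-week visit. It is 0 days if the site keeps the 30-day contact.

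4. **What the echocardiogram rule still forces.** Protocol 11.3.3 requires discontinuing subjects without a Visit 6 echocardiogram to have one at 30 days ± 1 week, that is days 23 to 37. This is 23 − 7 = 16 to 37 − 7 = 30 days after a day-7 visit. Such a subject must be seen again, which does not fit closing her at day 7. A subject who had the echocardiogram at Visit 6 has no such backstop.

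5. **Is pregnancy an exception anywhere?** No other section of either document makes it one. Sections 5.1 and 8.4 and footnote j expressly extend the 30-day timing to subjects who discontinue early.

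6. **Does any efficacy result move?** No. SAP Table 3-1 and SAP section 8 restrict seizure data to dates up to and including the last dose, so every diary day at risk lies outside the efficacy analyses.

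**The case against.** The strongest reply is that the texts can be read together. Section 11.1.4 speaks of an SFU Visit without calling it Visit 9, and it does not waive the 30-day contact. An early check after a possibly abrupt stop is clinically sensible. On that reading nothing is lost and only the label is poor. This reading is available, and it is why the lower end of the gap is 0. But the section does not state it, and a site should not have to infer that a second visit under the same name is still due.

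A second reply is that most of the safety information is protected elsewhere, and this largely stands:

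- SAEs are reported to 6 months after last intake (11.1.2.3).
- Ongoing adverse events are usually followed for 30 days after IMP stops (11.1.3).
- The pregnancy is followed to outcome and the child for 30 days after birth, with miscarriage, ectopic pregnancy, fetal demise and congenital anomaly handled as SAEs (11.1.4).
- Section 11.1.1.1 extends adverse event recording over post-treatment periods that the protocol requires.

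A reader might infer that serious events or pregnancy outcomes would be missed. The documents do not support that.

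A third reply concerns 11.3.3, where the closing paragraph asks for the SFU Visit within about a month. A day-7 visit would satisfy that wording, and the paragraph follows text on echocardiogram-driven withdrawals. It is weak evidence for a 30-day rule, and the case does not need it.

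Finally, one might want to add withdrawal scoring for subjects who stop without tapering, because Visit 8 has the instruction "Obtain CIWA-B data only for subjects tapering". That is a separate preference. It is also arguable whether tapering there simply means not converting to the extension, since Table 5-1 carries no such limit.

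**Conclusion.** The inconsistency is real and is in current text. Section 11.1.4 gives a timing for the SFU Visit that conflicts with the single 30-day visit set for all subjects outside the extension, including early discontinuations.

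Its size is 0 to 23 days of recording of new non-serious adverse events and diary entries per affected subject. The upper end is a worst case. It needs the site to treat the 1-week visit as a replacement for Visit 9 and to close the subject there, and it should not be read as an expected loss.

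The documents give no number of affected subjects. Few are expected, because contraception is required and inclusion criterion 10 calls for a negative pregnancy test before first dosing and "prior to further dispensing at each study visit thereafter".

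It would go too far to say that the trial's safety results or any efficacy conclusion is at risk. The SAP's Taper and Safety Follow-up period ends at final contact, so an early closure would shorten that period for the subject concerned without breaking any analysis. Type I error and sample size are unaffected. This is a minor correction worth making.

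**What to change.** Replace the 11.1.4 bullet with: *The SFU Visit (Visit 9) should be scheduled 30 days after the last IMP intake; any 1-week contact after IMP discontinuation is in addition to, and does not replace, Visit 9, and AE and diary recording continue to Visit 9.*

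This keeps an early check possible, restores the common end point, and needs no change to the SAP. A full Visit 8 assessment set, or an extra withdrawal score for subjects who stop without taper, is optional and not part of the correction.

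The cost is one sentence in an amendment or administrative letter. For a site that had been treating the 1-week visit as the only one, it is at most one standard follow-up visit per affected subject, and section 5.1 already requires that visit.
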